6.4 Blood sampling (total of 40ml)

20ml for standard of care : FBC, LFTs, renal function, CRP and ESR (if not performed within the last one month). *HLA-B27* if not previously performed.

20ml if subjects consent to the research element of the study : for storage and later analysis (serum biomarkers, proteomics and genotyping).

6.5 Stool sample

If subjects consent to the research element of the study, a stool collection kit for faecal calprotectin testing will be provided (if not performed within the last one month) and a further sample will be stored for future microbiome analysis.

6.6 Dedicated axial MRI Scan

This will be requested during the first clinic consultation (cases and controls ; funded by the NHS or research grant as appropriate)

6.7 Definition of the end of study

This will be the date of the last visit of the last participant

If a subject is unable to undertake these assessments immediately, a convenient future research clinic appointment will be made for them and associated travelling costs will be reimbursed.

This study schedule will pose low burden and inconvenience to the subject. Blood sampling will take place at the time of clinical measurements, and are of low total volume (40ml). The subjects will be asked to return to have the dedicated axial MRI scan and to minimise inconvenience, they will be encouraged to return their stool samples when they attend for the scan. Control subjects will be reimbursed for travel and parking costs, and the case subjects will also be reimbursed for any extra travel or parking costs incurred through participating in the study.

Clinical questionnaires are those that would be completed *as per* standard in usual clinical care (except for the control group). However, as we are asking questions in some of the PROMs about the subject's experience of illness, this may cause a degree of upset. Therefore to minimise distress, the clinician ([name]) will talk the subject through each questionnaire prior to completion at the initial clinic visit. In addition, our participation information sheets will stress that participation is voluntary and that the subject can withdraw from the study at any time without their care being affected. Our participation information sheets will also explain the processes taken to maintain anonymity and confidentiality.

The correspondence (invitation letters and PIS) for CD subjects with and without known SpA will have different content to reflect this and to reduce any potential concern or anxiety.

The MRI scan is a non-invasive procedure and the subjects will already have had the experience of having a MRI scan (MRE). However, some subjects may find it difficult to have the MRI scan if they suffer from claustrophobia. Therefore, the MRI scan procedure will be explained to the subject during the initial consultation and they will be provided with the opportunity to ask any questions. We will also emphasise that this is voluntary and that they have the right to decline this or any other part of the study.

7. Data collection, source data and confidentiality

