4.3 ProSpA-CD-Assess phase

4.3.1 Assessment of patients with lesions on MRE consistent with axSpA (cases)

Patients with lesions on MRE consistent with axSpA (and no known diagnosis of SpA) will be informed by telephone and letter by the gastroenterology team and referred to [name] NHS rheumatology SpA clinic. They will also be sent separately an invitation letter, participant information sheet (PIS) and reply slip (study interest form with a stamped-addressed envelope for returns) for the ProSpA-CD-Assess phase of the study by the gastroenterology team. CD subjects with a known diagnosis of SpA who are already under review by rheumatology and who have lesions on MRE consistent with axSpA will also be considered as cases and will be sent an invitation letter, PIS and study interest form. However, they will instead be invited to attend the rheumatology SpA research clinic to be assessed for axSpA (with the control group) as this will be considered to be outside of their routine NHS care.

In the NHS SpA clinic, the patients will be assessed by a single rheumatologist ([name], in a supernumerary capacity with salary funded by the research grant) for clinical evidence of axSpA *as per* standard of care using the 2009 ASAS criteria for axSpA, modified New York criteria for AS and CASPAR criteria for PsA (see Appendices 5, 6 & 7). The assessment will include a clinical history, examination (including BASMI, 68 tender joint count, 66 swollen joint count, the SPARCC enthesitis index and for skin or nail psoriasis), PROMs (BASDAI, BASFI, VASbp, ASDAS and HAQ-DI), blood samples (FBC, renal function, LFTs, CRP and ESR unless performed in the preceding month, and HLA-B27 unless previously performed) and stool samples (the monitoring of IBD luminal activity with faecal calprotectin is well established [41, 42]; stool samples will therefore also be collected to measure faecal calprotectin concentrations unless performed in the preceding month). During the consultation, the ProSpA-CD-Assess phase of the study will also be discussed further and patients will be provided with the opportunity to ask any questions they may have regarding the study. If they agree to participate in the study and meet the inclusion criteria, then written informed consent will be taken. The blood and stool tests will be performed as per standard of care if clinically indicated or for research and funded by the research grant if not clinically indicated.

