4.3.2 Assessment of subjects with no lesions on MRE consistent with axSpA (controls)

Subjects (including those with a known diagnosis of SpA) who have consented to having their MRE scans reviewed, but who do not have lesions consistent with axSpA, will be informed in writing of this by the gastroenterology team. They will also be advised that they may be invited to enter the study as a control subject if they are randomly selected through matching (age and sex) to the enrolled 'MRE+ cases' (1:1 ratio). Matched potential control subjects will then be sent an invitation letter, PIS and reply slip (study interest form with a stamped-addressed envelope for returns) by the gastroenterology team to attend the rheumatology SpA research clinic to be assessed by [name] for clinical evidence of axSpA. CD subjects with a known diagnosis of SpA who are already under review by rheumatology and who have lesions on MRE consistent with axSpA will also be invited to attend this clinic for review outside of their routine NHS care but will be considered as cases. Informed consent for study participation in the SpA research clinic will be performed at the start of the consultation. The same clinical assessments, blood and stool samples and dedicated axial MRI scan of the spine and sacroiliac joints will be performed in this control group and in the group of CD subjects with a known diagnosis of SpA who are MRE+ as in the other cases, but will be funded by the research grant unless clinically indicated.

Control subjects in whom there is no evidence of axSpA (by ASAS, modified New York or CASPAR classification criteria) will be informed by letter, which will also be copied to the subjects GP and gastroenterology consultant. Control subjects who do have evidence of axSpA will be informed by letter (also copied to GP and gastroenterology consultant) and asked to return to [name] NHS rheumatology SpA clinic for ongoing care. CD subjects who already have a diagnosis of SpA (both in the control group and cases group) and are already under review by a rheumatology team will be informed by letter of the research clinic outcome and will be followed up as planned by their primary rheumatology team. We will also send a copy of the clinic letter to their GP, gastroenterology consultant and named rheumatology consultant to inform them of the clinic findings and to notify them of any outstanding tests/ management plans that may need to be considered at the next clinic review.

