be part of their standard NHS care. PROMs for the control group and group of CD subjects with a known diagnosis of SpA in the SpA research clinic will be labeled with the subjects unique study identification code only as this will be outside of their routine NHS care. The blood tests (FBC, renal function, LFTs, CRP, ESR, HLA B27), stool sample for faecal calprotectin and dedicated axial MRI scan of the spine and sacroiliac joints for all subjects within the study will be labeled as per standard trust policy with subject details (name, date of birth, hospital number) and will be requested, reported and stored on the Epic system. Where these tests are performed for research purposes and not standard of care, we will receive written consent from the subject for this. The extra blood and stool samples taken for storage and future analysis for all subjects will be labeled with the unique subject study identification code only. When the subject data is transcribed on to the secure password protected electronic Microsoft-Access database (for all subjects in the study) it will be assigned to the appropriate unique subject study identification code which will be linked to the subject's hospital number. All other identifiable data (such as name, date of birth and NHS ID number) will be removed. This will only be accessible to the investigator team. [name] is the 'Data Protection Officer' for CUH NHSFT.

Cambridge University Hospitals NHSFT will comply with all aspects of the Data Protection Act 1998 and operationally this will include:

- 7.1.1 Consent from subject to record personal details including name, date of birth, address and telephone number, NHS identification number, hospital identification number, GP name and address.
- 7.1.2 Appropriate storage, restricted access and disposal arrangements for the subjects personal and clinical details.
- 7.1.3 Consent from subject for access to their medical records by responsible individuals from the research staff, the sponsor or from regulatory authorities, where it is relevant to study participation.
- 7.1.4. Consent from subject for the data collected for the study to be used to evaluate safety and develop new research.

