8.2 Statistical analysis

Statistical input has been sought from the University of Cambridge Statistics Clinic (PhD student [name] and his supervisor [name]) and will be supported by [name]. Inter- and intra-rater reliability testing will be performed for the MRE and axial MRI assessments using intra-class correlation coefficients (ICC). The proportion of CD cases with evidence of axSpA on MRE imaging who fulfil diagnostic criteria for axSpA will be expressed as a percentage. Further descriptive analyses will also be performed on study participants. Due to the possible preponderance of patients with axial pain willing to participate in the study and therefore selection bias, we will not be able to calculate the true prevalence of axSpA in CD patients.

As it is expected that the majority of data collected will be count data with an excess of zero-values, a zero-inflated Poisson (ZIP) regression model will be used to test for association between the presence of axSpA, MRE score, PROMs, clinical indices, site of CD and blood biomarkers. In addition, ZIP regression will be used to test for association between MRE scores and those of dedicated axial MRI scans. Zero-inflated binomial regression will be used as appropriate, where the mean approximates the variance. Two-tailed tests will be performed, and the alpha set at 0.05.

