8.3 Missing data

If a subject is uncertain how to complete an outcome measure questionnaire correctly, a research professional will be present to provide support and ensure correct and full completion.

9. Ethical considerations

The study will be performed in accordance with the recommendations guiding ethical research involving human subjects adopted by the 18th World Medical Assembly, Helsinki, Finland, 1964, amended at the 52nd World Medical Association General Assembly, Edinburgh, Scotland, October 2000. Informed written consent will be obtained from the patients prior to registration into the study.

Any treatments prescribed for patients within the study who have a diagnosis of axSpA will be in accordance to existing local and clinical commissioning group (CCG) treatment pathways, and will not in any way favour the funder's (MSD) product, namely golimumab (Simponi; an anti-tumour necrosis factor alpha product).

The study will be submitted for approval by the local Research Ethics Committee (REC) via the Integrated Research Application System (IRAS). Ethics approval from the (institutional review board) research and development department of CUH NHSFT will also be sought.

The right of a patient to refuse participation without giving reasons will be respected. The patient will remain free to withdraw at any time from the study without giving reasons and without prejudicing his/her further treatment.

10. Statement of indemnity

Cambridge University Hospitals NHSFT is able to provide insurance to cover for liabilities and prospective liabilities arising from negligent harm. Insurance cover is not provided for claims arising from non-negligent harm. Clinical negligence indemnification will rest with the CUH NHSFT under standard NHS arrangements.

11. Safety

[figure not shown]
Venepuncture is the only potential risk to patients in this study. The healthcare professionals performing this procedure are trained in venepuncture and will also be able to deal with any potential complications. There are no other significant potential risks from the study procedures.

12. Costings

The study will be funded by MSD (Merck, Sharp and Dohme corporation) who have committed £147,273 for the study. This will fund [name] salary for the 24 months of the study, research axial MRI scans, research blood tests and stool sampling, consultant radiologist time to review the dedicated axial MRI scans twice, statistical support and office ancillaries.

13. Appendices

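### The clinician's unscripted talk-through before each questionnaire leaves an avoidable route by which MRE group could influence the patient-reported scores

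*Combined protocol and SAP*

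**What the plan says.** The PROMs are BASDAI, BASFI, VASbp, ASDAS and HAQ-DI (section 6.2). Section 6 notes that some of their questions may upset subjects and gives the remedy, "Therefore to minimise distress, the clinician" "will talk the subject through each questionnaire prior to completion at the initial clinic visit". The rule covers each questionnaire and does not distinguish cases from controls. No script is described.

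On who assesses whom, section 4.3.1 says of MRE-positive subjects without known SpA: "In the NHS SpA clinic, the patients will be assessed by a single rheumatologist". Section 4.3.2 has matched controls invited "to attend the rheumatology SpA research clinic to be assessed by [name] for clinical evidence of axSpA". MRE-positive subjects with known SpA attend that same research clinic but count as cases. Section 4.2.1 describes blinding or anonymisation for the reading of MRE images. The plan states no blinding for the clinical assessor.

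On use of the scores, section 4.1 ends the Assess phase with a comparison of the two groups, and section 8.2 uses zero-inflated regression to "test for association between the presence of axSpA, MRE score, PROMs, clinical indices, site of CD and blood biomarkers". Section 8.3 adds that, for a subject unsure how to fill in a form, "a research professional will be present to provide support and ensure correct and full completion".

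**The concern.** A self-report score is useful beside the clinician's findings because it comes from the subject. Here a person who will usually know the MRE group explains the instrument, in unfixed words, just before it is filled in. How a term such as stiffness or back pain is explained can move the answers. If the explanation differs between MRE-positive and MRE-negative subjects, even unintentionally, the scores differ for a reason unrelated to symptoms.

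What is at stake is the set of secondary association analyses in section 8.2 that involve PROMs. No regression on the collected data can separate an effect of how the forms were introduced from a true difference in symptoms, so the protection has to lie in the procedure.

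**Working it through.** The plan gives no figure to reproduce on this point. The check traces the procedure, followed by two illustrations.

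**1. Can the clinician usually tell the group?** Attendance at the NHS clinic means MRE-positive. The research clinic holds all the controls plus the cases with known SpA. Let f be the share of cases with known SpA, which the documents do not give. With 1:1 matching, reading NHS clinic as case and research clinic as control is right for all controls and for a share 1 − f of cases:

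½ + ½(1 − f) = 1 − f/2.

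The probability that a research-clinic subject is a control is 1/(1 + f).

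| f (assumed) | 0% | 10% | 20% | 30% | 50% |
|---|---|---|---|---|---|
| Group inferred correctly, 1 − f/2 | 100% | 95% | 90% | 85% | 75% |
| Control, given research clinic | 100% | 91% | 83% | 77% | 67% |

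So "usually" would be a fair description across this range, although attendance at the research clinic does not identify a control with certainty.

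**2. Is the explanation kept uniform?** Three safeguards were looked for: standard wording, an administrator unaware of the group, and completion before history and examination. None is stated. Section 6 lists questionnaires ahead of clinical measurements, while section 4.3.1 lists history and examination ahead of PROMs; neither is presented as a required order. The section 8.3 helper is not described as independent of the assessor or unaware of the group.

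**3. Do the scores enter a comparison by group?** Yes, through sections 4.1 and 8.2.

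**4. What would a shift do? (Illustration only.)** Inputs: 66 cases and 66 controls, the expected minimum in section 8.1; two-sided alpha 0.05 from section 8.2; no true difference; and an assumed spurious shift of d standard deviations. In a simple comparison of two means the standard error, in SD units, is √(2/66) = 0.174. With t = d/0.174, the rejection probability is Φ(t − 1.96) + Φ(−t − 1.96).

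| d (assumed) | 0 | 0.1 | 0.2 | 0.3 |
|---|---|---|---|---|
| t | 0 | 0.57 | 1.15 | 1.72 |
| False-positive rate | 5.0% | 8.9% | 21.0% | 40.7% |

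The noncentral t gives 8.8%, 20.7% and 40.2% for the three non-zero shifts. The plan specifies zero-inflated regression, not this test, and the same figures would follow from a shift of any origin. They show sensitivity to a shift and say nothing about whether this procedure produces one.

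**The case against.** The strongest reply is that one rule applies to cases and controls alike. An explanation common to both moves both groups equally, and nothing in the text says the clinician will explain the forms differently. That is correct as far as it goes: bias arises only if the talk-through is delivered or received differently by group. What stands is that the plan contains nothing to prevent or detect this.

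The talk-through also has a purpose of its own, to prepare subjects for upsetting questions, which section 8.3 support for uncertain subjects does not replace. That stands, and it means the reassurance should be kept and should come before completion.

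Subjects are also told their MRE result before they attend (sections 4.3.1, 4.3.2 and 5.2.1.2), so reporting bias from that knowledge exists whatever the clinician says. This stands too and limits the gain.

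A reader might infer more than the documents support:

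- That the clinician goes through every item or administers the forms. The text describes an explanation of each questionnaire, after which the subject completes it.
- That the identity of this clinician with the single assessor is stated. Names are removed, so it is an inference, though the natural one.
- That the clinical phenotype of eSpA is compromised. Objective 4 characterises it through extra-articular features, not PROM differences.
- That the 6-month scores are made non-comparable because the talk-through is specified only for the initial visit. Section 8.2 plans no analysis of PROM change.
- That form labelling adds bias. Research-clinic PROMs "will be labeled with the subjects unique study identification code only as this will be outside of their routine NHS care", while NHS-clinic forms carry patient details as part of standard care (section 7.1). The documents give no reason why a name or a code would alter symptom scores.

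**Conclusion.** The point holds as a procedural weakness in secondary analyses. As written, the plan lets an assessor who can usually infer MRE group introduce the self-report forms in unfixed words, and then tests the resulting scores against axSpA and MRE score. Whether a group-dependent shift would occur, and how large it would be, cannot be determined from the documents; the false-positive figures rest wholly on assumed shifts. Sensitivity and specificity rest on dedicated MRI with clinical assessment and are not directly affected.

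The conclusion assumes that the clinician in section 6 is the single assessor and that cases with known SpA are a minority, or at most about half, of all cases. The change is worth making because it is cheap and cannot be made after data collection, not because bias has been shown.

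**What to change.** In section 6, replace the open talk-through with one fixed, neutral introduction, identical for cases and controls. It should give the reassurance about possible upset and voluntary participation, and should not interpret items. Subjects then self-complete all PROMs immediately after consent and before history-taking and examination. Limit section 8.3 help to the same neutral wording. Use the same procedure at the 6-month visit for the cases who attend it; controls and cases with known SpA have no such study visit and need none for this purpose.

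This fits the research clinic, where consent is already taken at the start of the consultation (section 4.3.2). For the NHS clinic, section 4.3.1 says only that consent is taken during the consultation, so a line fixing the order is needed there.

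As a check with no new data collection, compare clinic BASDAI with the optional postal BASDAI (section 5.2.2.1), by group. The postal form precedes MRE review and clinician contact. Its stated use is to gauge selection bias, so the protocol should add this use and keep the response format the same. A difference between groups in the change from postal to clinic score would also include the effect of learning the MRE result and any real change over time, so it can flag a shift but cannot attribute it.

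Cost: a short text and wording changes in sections 4.3.1, 6 and 8.3, with no extra staff or visits. The downside is less individual preparation of subjects and possibly a few more queries or missing items.

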7.1 General

All information collected during the course of the study will be kept strictly confidential.

Each subject will be assigned a unique subject study identification code which will be linked to their hospital number on a secure password protected electronic Microsoft-Access database and stored on the Cambridge University Hospitals NHS Foundation Trust (CUH NHSFT) computer network.

The clinic encounter for the cases in the NHS SpA clinic will be documented on to the CUH NHSFT electronic health record system (Epic) and a letter will be sent out to the patient, their GP and gastroenterology consultant to summarise this encounter. The clinic encounter for the controls and CD subjects with a known diagnosis of SpA in the SpA research clinic will also be documented on the Epic system and a letter will be generated from this clinic to the subject, GP, gastroenterology consultant and rheumatology consultant if appropriate. For the cases in the NHS SpA clinic, the PROMs will be labeled with the patient's details (name, date of birth and hospital number) as this will

be part of their standard NHS care. PROMs for the control group and group of CD subjects with a known diagnosis of SpA in the SpA research clinic will be labeled with the subjects unique study identification code only as this will be outside of their routine NHS care. The blood tests (FBC, renal function, LFTs, CRP, ESR, HLA B27), stool sample for faecal calprotectin and dedicated axial MRI scan of the spine and sacroiliac joints for all subjects within the study will be labeled as per standard trust policy with subject details (name, date of birth, hospital number) and will be requested, reported and stored on the Epic system. Where these tests are performed for research purposes and not standard of care, we will receive written consent from the subject for this. The extra blood and stool samples taken for storage and future analysis for all subjects will be labeled with the unique subject study identification code only. When the subject data is transcribed on to the secure password protected electronic Microsoft-Access database (for all subjects in the study) it will be assigned to the appropriate unique subject study identification code which will be linked to the subject's hospital number. All other identifiable data (such as name, date of birth and NHS ID number) will be removed. This will only be accessible to the investigator team. [name] is the 'Data Protection Officer' for CUH NHSFT.

Cambridge University Hospitals NHSFT will comply with all aspects of the Data Protection Act 1998 and operationally this will include:

- 7.1.1 Consent from subject to record personal details including name, date of birth, address and telephone number, NHS identification number, hospital identification number, GP name and address.
- 7.1.2 Appropriate storage, restricted access and disposal arrangements for the subjects personal and clinical details.
- 7.1.3 Consent from subject for access to their medical records by responsible individuals from the research staff, the sponsor or from regulatory authorities, where it is relevant to study participation.
- 7.1.4. Consent from subject for the data collected for the study to be used to evaluate safety and develop new research.

